### **Study Endpoints**

#### **Primary Endpoints**

- Number of days since admissions to clinical recovery
- Change in IL-6 levels from baseline to Week 2.
- Percentage of patients with disease progression by Week 2 based on WHO 9-point ordinal scale

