### **Statistical analysis**

**Randomization: Subjects** will be randomized in a 1:1 ratio to:

- 83.91 mg zinc acetate (Zinc+NM) QD + standard of care for 2 weeks
- Standard of care for 2 weeks

**Determination of sample Size:** Sample size calculations are aimed at comparisons of days to clinical recovery between zinc supplementation and standard of care alone. Assuming alpha = 0.05 and a 10% dropout rate, randomization of 60 subjects will

provide 80% power to detect a difference in time to recovery between arms of 3 days assuming a SD of 4 days. This sample size will also provide at least 80% power to detect a change in percentage of people with clinical progression of 5% based on an estimated

clinical progression rate of 20% in the standard of care arm.

**Analysis Populations:** The analysis population for efficacy will be per protocol which includes all randomized subjects who complete 2 weeks of therapy and/or return for Week 2 visit. All safety analyses will include all randomized subjects who are

administrated at least 1 packet of the investigational product.

**Baseline Characteristics:** Demographics and Baseline characteristics will be summarized descriptively by group and overall using per protocol population. The following Baseline

characteristics will be summarized: sex, race, age, comorbidities, ethnicity

**Clinical Laboratory Assessments:** Blood chemistry, hematology parameters will be summarized at Baseline as well as visit 3 and 4. Laboratory values at Baseline and subsequent changes in laboratory values will be summarized descriptively overall and

by therapy group.

**Vital signs:** Vital sign measurements will be summarized at Baseline, Week 2 and Week 4. In addition, changes from Baseline to Week 2 or 4 will be summarized. For each summary the number, mean, median, standard deviation, minimum, and maximum

values will be presented overall and by therapy group.

**Safety Analyses:** All safety analyses will be based on the Safety Population, comprising all subjects who are randomized to the therapy group and subsequently receive at least one packet of investigational product. Safety assessments will be analyzed by frequency of events/abnormalities for categorical values or summarized using descriptive statistics

(mean, standard deviation, median, range, and number of observations).

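### The plan's claim of at least 80% power for a 5% change in disease progression is false: with 60 patients, power for 20% versus 15% is about 7%, and no reading of the 5% reaches 80%.

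*Combined protocol and SAP*

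**What the plan says.** Under Statistical analysis, the sample-size paragraph first addresses days to clinical recovery. With alpha 0.05, 10% dropout and 60 patients randomised, the trial is said to "provide 80% power to detect a difference in time to recovery between arms of 3 days assuming a SD of 4 days". It then makes a second claim: "This sample size will also provide at least 80% power to detect a change in percentage of people with clinical progression of 5" percent. The starting point is an assumed "clinical progression rate of 20% in the standard of care arm".

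No test or sidedness is given for either statement. Allocation is 1:1, and both the project aims and the Study Design section make 60 the total for the two arms. The paragraph on dropouts and missing data removes patients without primary endpoint data from the analysis.

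Progression is not a side remark in this plan. The Primary Endpoints list includes "Percentage of patients with disease progression by Week 2 based on WHO 9-point ordinal scale", and the primary objective names it as well.

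**The concern.** A 5-point difference between two proportions near 20% is small, and trials that can detect it usually have many hundreds of patients per arm. A claim of 80% power with about 27 per arm is therefore implausible on its face.

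The claim is attached to a primary endpoint. Anyone who relies on it, whether ethics committee, funder or reader of the results, would take a non-significant progression comparison as fairly informative. At the true power, a real fall from 20% to 15% would be missed more than nine times in ten.

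**Working it through.** **Inputs, all from the plan.** 60 randomised, 1:1, alpha 0.05, 10% dropout, progression 20% under standard of care, change of 5%. Evaluable per arm: 30 × 0.9 = 27. Two-sided testing is my assumption; one-sided results are shown beside it.

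**Step 1: the recovery claim.** For two means, power = Φ(δ / (σ√(2/n)) − 1.96), with δ = 3 and σ = 4.
- n = 27: 3 / (4 × 0.2722) = 2.756; 2.756 − 1.960 = 0.796; power 78.7%.
- n = 30: 2.905 − 1.960 = 0.945; power 82.8%.

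This approximately reproduces the stated 80%.

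**Step 2: the progression claim, 20% versus 15%.** With pooled variance under the null,

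power = Φ( [d√n − 1.96√(2p̄(1−p̄))] / √(p₁(1−p₁) + p₂(1−p₂)) ),

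where d = 0.05 and p̄ = 0.175, so √(2 × 0.175 × 0.825) = 0.5374 and √(0.16 + 0.1275) = 0.5362.
- n = 27: (0.2598 − 1.0532) / 0.5362 = −1.480; power 6.9%.
- n = 30: (0.2739 − 1.0532) / 0.5362 = −1.453; power 7.3%.

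These count rejections in the favourable direction only; adding the other tail gives 7.7% at n = 27.

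**Step 3: patients needed for 80%.** n = [1.96 × 0.5374 + 0.8416 × 0.5362]² / 0.05² = (1.0532 + 0.4513)² / 0.0025 ≈ 906 evaluable per arm. With 10% dropout, 906 / 0.9 ≈ 1,007 randomised per arm. One-sided: 714 evaluable per arm.

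**Step 4: other readings and other tests.** Each cell gives power at 27 / 30 per arm.

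| Reading of the 5% | Normal approx., two-sided | Normal approx., one-sided | Exact power, uncorrected chi-square | Exact power, Fisher two-sided | Evaluable per arm for 80%, two-sided |
|---|---|---|---|---|---|
| 20% to 15% | 6.9% / 7.3% | 12.2% / 12.8% | 8.5% / 7.9% | 3.0% / 3.7% | 906 |
| 20% to 25% | 6.4% / 6.7% | 11.4% / 11.8% | 8.0% / 7.3% | 3.3% / 3.9% | 1,094 |
| 20% to 5% | 38.2% / 41.7% | 50.9% / 54.6% | 41.5% / 45.3% | 19.0% / 24.1% | 76 |
| 20% to 19% (5% relative) | 3.1% / 3.1% | 6.0% / 6.1% | not run | not run | 24,641 |

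The best cell in the table is 54.6%.

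**Step 5: precision.** Expected 95% confidence interval half-width at 27 per arm: 1.96 × √((0.16 + 0.1275) / 27) = 1.96 × 0.1032 ≈ 0.20. That is 20 percentage points, four times the 5-point difference.

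**The case against.** The best defence is that the trial was never sized on progression. The paragraph says its calculations are aimed at days to recovery, and that part approximately holds. This stands, and it limits the finding: a reader might infer that 60 patients has no justification at all, and the documents do not support that. It does not rescue the second sentence, which makes its own quantified claim.

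It is also fair that sidedness and test are not stated, so 7% and 906 are conditional figures. The range across tests and sides has to be given, but nothing in it approaches 80%. One combination does get there: a fall to 5%, tested one-sided, with 60 patients per arm, gives about 81%. The plan rules this out by making 60 the two-arm total.

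Three further inferences go too far.
- That the progression comparison could hardly detect anything: if no patient on zinc progressed (20% versus 0%), two-sided power would be about 70% to 75%.
- That the trial team will certainly read a null progression result as no effect: the Limitation paragraph does say that finding no benefit would mean low zinc follows from inflammation, so the risk is credible. But that remark concerns benefit in general, not progression.
- That progression must stop being a primary endpoint: low power does not by itself require this, and it would alter the primary objective and the endpoint list.

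**Conclusion.** The progression power statement is wrong as written and must be corrected, because it gives a false figure for a primary endpoint. Under two-sided alpha 0.05 and about 27 evaluable per arm, power for 20% versus 15% is about 7% (3% to 9% across tests; 12% to 13% one-sided by the normal approximation), against a claim of at least 80%. The most generous reading, a fall to 5%, gives 38% to 42% two-sided by the normal approximation, 19% to 24% by Fisher's exact test, and 51% to 55% one-sided.

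The exact figures depend on the assumed sidedness and test; the conclusion does not. The error is confined to this sentence and leaves the recovery calculation untouched.

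**What to change.** Delete the sentence and replace it with wording such as:

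> The sample size is based on days to clinical recovery. With about 27 evaluable patients per arm, power to detect 20% vs 15% progression is about 7% (two-sided alpha 0.05, normal approximation), and about 38% for 20% vs 5%. Progression will be reported as a between-arm difference with its 95% CI (expected half-width about 20 percentage points), and a non-significant result will not be read as evidence of no effect.

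If the sponsor intends one-sided testing or a specific test, name it and give the power that goes with it.

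Cost: a stated figure becomes less favourable; no extra patients, visits or data are needed. Moving progression to the secondary endpoints is a separate design choice for the sponsor. It would change the primary objective and endpoint list, so it is more than a change of wording and is not required here.

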### **1) Clinical trial objectives**

#### **Primary objective**

To evaluate the effectiveness of oral zinc supplementation (83.91 mg zinc acetate) Zinc+NM QD (80mg Zn2+) QD as compared to placebo as compared to control group without zinc supplementation to reduce IL-6 increase in the course of SARS-CoV-2 infection, to decrease days to clinical recovery and to decrease the percentage of people with COVID-19 who have disease progression by Week 2, defined as inpatients, worsening of  $\geq 1$  level on the WHO 9-point ordinal scale

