### **Study Design**

This is a randomized, open-label clinical study evaluating the effectiveness of zinc supplementation as compared to standard of care on need disease severity and on IL-6

levels in people with COVID-19. Subject eligibility will be based on inclusion and exclusion criteria

**Population of study:** Sixty eligible adult subjects at one clinical site in Spain (Hospital del Mar) will be randomized in a 1:1 ratio to:

- ~~Zinc acetate 80mg QD~~ 83.91 mg zinc acetate (Zinc+NM) QD + standard of care for 2 weeks
- Standard of care for 2 weeks

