**Adverse events:** Adverse events will be coded using the Medical Dictionary for Regulatory Activities (MedDRA) coding dictionary. Adverse events will be defined as any event with a start date occurring on or after initiation of therapy on Day 1 or, if pre-existing, worsening after initiation of therapy on Day 1. The incidence of AEs will be

summarized by body system and MedDRA preferred term, overall and by therapy group.

If a subject reports the same AE more than once, then that subject will only be counted once for the summary of that AE, using the most severe intensity.

**Handling of Dropouts or Missing Data :** Dropouts or participants missing data for the primary endpoints will be excluded from the analysis.

**Limitation:** We might find no benefit in COVID-19 patients supplemented with zinc. That would mean that the low zinc levels detected in COVID-19 patients with worse prognosis are a consequence of the inflammatory status. The results will be also very helpful for physicians worldwide.

- **To study the immune responses of the COVID-19 patients enrolled in the clinical trial (Subproject 2)**

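### Both safety-population definitions require a packet of study product, so no standard-of-care patient qualifies and the planned by-arm adverse event table would have no control column.

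*Combined protocol and SAP*

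**What the plan says.** The Statistical analysis section defines the safety population twice.

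- The Analysis Populations paragraph takes all randomised subjects who are "administrated at least 1 packet of the investigational product".
- The Safety Analyses paragraph bases every safety analysis on a Safety Population "comprising all subjects who are randomized to the therapy group and subsequently receive at least one packet of investigational product".

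The Study Design section describes the trial as follows: "This is a randomized, open-label clinical study evaluating the effectiveness of zinc supplementation as compared to standard of care". The treatment arm is "83.91 mg zinc acetate (Zinc+NM) QD + standard of care for 2 weeks". The control arm is "standard of care for 2 weeks", with nothing added to it. The same two arms are listed again under Randomization in the Statistical analysis section.

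The Adverse events paragraph fixes the starting point: "Adverse events will be defined as any event with a start date occurring on or after initiation of therapy on Day 1". Adverse event incidence is then to be "summarized by body system and MedDRA preferred term, overall and by therapy group". The Safety Endpoints section names the incidence of adverse and serious adverse events and does not limit it to one arm.

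**The concern.** Control patients receive no packet, so a population that requires one excludes all of them. The plan nevertheless asks for adverse events by group, which needs both arms. The population rule therefore defeats the display it is meant to support.

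What is at stake is interpretation. The participants are inpatients with COVID-19, and the plan's own Secondary Endpoints treat diarrhoea, dyspnoea and temperature as signs of the disease. If such an event is reported on zinc, the natural question is how often it occurred over the same days in patients randomised to standard of care. The trial records what is needed to answer that, but the population definition would keep it out of the adverse event analysis.

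**Working it through.** The plan gives no figure for the size of the safety set, so there is none to reproduce. The check applies each definition to each arm.

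**Inputs.** Sixty subjects randomised 1:1 (Study Design), which is 60 / 2 = 30 per arm. Packets of study product: zinc arm yes, control arm none (arm lists in Study Design and in Statistical analysis).

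**Step 1: who qualifies.**

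| Definition | Zinc arm | Standard-of-care arm |
|---|---|---|
| Analysis Populations: randomised and given a packet | up to 30 | 0 of 30 |
| Safety Analyses, if *therapy group* means the zinc arm | up to 30 | 0 of 30 |
| Safety Analyses, if *therapy group* means either arm | up to 30 | 0 of 30 |

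The result does not depend on how *therapy group* is read. The packet condition alone excludes the controls.

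**Step 2: what the adverse event table would contain.** The zinc column has a denominator of up to 30 and the standard-of-care column has 0. The overall column is 30 + 0 = 30, identical to the zinc column. At least 30 / 60 = 50% of those randomised contribute nothing to it.

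**Step 3: what one arm can show.** If an event is seen in none of 30 zinc patients, the one-sided 95% upper limit for its rate is 1 − 0.05^(1/30) = 0.095, or 9.5%. An incidence and its limit can therefore be reported. What is missing is a rate from concurrent controls to set beside it.

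**Step 4: are control events recorded?** Task 1.1.1 lists adverse event recording at Visit 2 (Day 7 ± 2) and Visit 3 (Day 14 ± 2), without restriction by arm. Visit 4 (Day 28 ± 4) lists laboratory tests, PBMCs and blood samples, and no adverse event review. Control data are thus planned up to Visit 3.

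**Step 5: is there a common start?** The onset rule refers to starting therapy on Day 1. The Study phases section equates Day 1 with baseline and randomisation, so the same date exists for both arms.

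**Step 6: after correction.** Zinc patients with a packet (up to 30) plus all patients randomised to standard of care (30) give up to 60, and both columns can be filled.

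**The case against.** The strongest reply is that this is loose drafting and the intention is clear. The plan uses *therapy group* for either arm in its laboratory, vital-sign and adverse event displays, one of the two definitions starts from all randomised subjects, and adverse events are recorded without regard to arm. A sensible analyst would include the controls. This supports the view that a comparison was meant, but it does not rescue the text, because both definitions carry the packet condition.

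A second reply is that the Primary objective mentions a placebo, so controls might receive packets. The wording there is "as compared to placebo as compared to control group without zinc supplementation", where two comparators stand side by side. The open-label design and both arm lists contain no placebo.

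Some stronger conclusions that a reader might draw do not hold:

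- *That control patients disappear from all safety output.* The laboratory and vital-sign paragraphs name no analysis population and are planned by group. The exclusion is firm only for what is analysed on the Safety Population.
- *That the safety endpoint cannot be answered.* Zinc-arm incidence can be reported as written. The objectives state no comparative safety aim, and the planned safety summaries are descriptive. The loss is the background rate.
- *That the adverse event definition has no meaning for controls.* Day 1 is the randomisation day, so the rule needs clarifying rather than replacing.
- *That adverse events are collected at every visit, so rewording alone gives reporting to Day 28.* Visit 4 schedules no adverse event review.
- *That an expected number of deaths can be attached.* The Preliminary results give mortality in two groups of a retrospective cohort. The documents do not say that these groups split exactly at the stated zinc cutoff, or that trial patients would resemble that cohort.

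**Conclusion.** The point holds. As written, the safety population is at most 30 zinc patients and none of the roughly 30 controls, and the adverse event table by arm cannot be produced as planned. This is a stated rule that gives the wrong result, not a missing detail, and it should be corrected before analysis. No primary endpoint is affected.

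The conclusion rests on two readings of the documents: that controls receive no packet, as both arm lists show, and that the packet condition is applied literally. The figure of 30 per arm assumes that 1:1 randomisation of 60 gives equal arms.

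**What to change.** 1. In both the Analysis Populations and the Safety Analyses paragraphs, use one identical definition: all patients randomised to zinc who received one or more packets, plus all patients randomised to standard of care.
2. In the Adverse events paragraph, count onset or worsening from Day 1 (baseline/randomisation) in both arms.
3. Report adverse events by arm over the period in which they are recorded, that is up to Visit 3 (Day 14).
4. If reporting to Day 28 is wanted, add an adverse event review to Visit 4 for both arms.

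Items 1 to 3 change wording only, since the recording they need is already scheduled without restriction by arm. Item 4 adds a procedure to an existing visit, at small extra cost.

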### **3. PRELIMINARY RESULTS:**

Our preliminary results are shown in the work entitled “**Low zinc levels at clinical admission associates with poor outcomes in COVID-19**” (13) which is the result of a tight collaboration between the laboratory of [name] (Hospital del Mar) and those of [name] and [name] (both at DCEXS, UPF).

This work aimed to focus clinical attention on serum zinc content (SZC) in COVID-19 patients. Our analysis showed a robust correlation between low SZC with COVID-19

severity and mortality. The cause is likely to be a combination of immune system imbalance and a direct benefit of viral replication.

A summary of the results obtained:

- In our retrospective observational study with 249 COVID-19 patients, **23% of the patients had at admission SZC lower than 50µg/dl**, the cutoff associated with ZD and development of clinical signs.
- Our study showed that **low SZC correlates with higher IL-6 and C-reactive protein at admission**, higher peak IL-6 during the episode.
- We detected in the low SZC group that subjects needed higher time to recover (25 days) versus the control group (8 days). In the same direction, the **mortality in low SZC patients was higher (21%) than in the control group (5%)** with normal zinc concentration.
- **SARS-CoV2** Infections in cell culture demonstrated that **low zinc levels favors SARS-CoV2 viral expansion** in the infected cells.

These results highlighted the urgent need to start clinical trials supplementing with zinc low SZC patients at admission to reestablish zinc homeostasis in order to study the cause-effect association between zinc nutritional status and COVID-19 progression. We expect with this new project that zinc supplementation in low SZC COVID-19 patients will

balance what has been called the cytokine storm caused by SARS-CoV-2 and as a consequence will reduce COVID-19 severity and mortality.

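### Efficacy is analysed only per protocol with missing primary data excluded, so deaths before Week 2 go uncounted and inclusion depends on what happens after randomisation

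*Combined protocol and SAP*

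**What the plan says.** Under Analysis Populations in the Statistical analysis section, the efficacy set is "per protocol which includes all randomized subjects who complete 2 weeks of therapy and/or return for Week 2 visit". Under Handling of Dropouts or Missing Data, "Dropouts or participants missing data for the primary endpoints will be excluded from the analysis". Under Baseline Characteristics, demographics and baseline data are "summarized descriptively by group and overall using per protocol population".

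This document contains no all-randomised efficacy analysis, imputation, sensitivity analysis or censoring rule, and no rule for death or non-recovery. The three primary endpoints (Study Endpoints) are a count of days to recovery, the IL-6 change to Week 2, and progression by Week 2 on the WHO scale. Follow-up ends at Day 28 (Study phases). The trial is open-label (Study Design).

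**The concern.** The two rules together decide who is analysed from what happens after randomisation. A patient who dies before the Week 2 visit has neither finished the course nor attended, so leaves the set for all three primary endpoints. That patient also has no Week 2 IL-6 value. The worst possible course is then not counted as progression.

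A survivor not recovered by Day 28 has no number of days to recovery. The plan does not say whether that is missing data or a censored observation. If it is treated as missing, the exclusion rule removes that patient too.

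Randomisation protects the comparison only if the patients analysed are those who were randomised. Once outcome influences inclusion, the arms can differ for reasons other than zinc. Task 1.1.2 expects the trial to prove an effect on severity and mortality and to yield a hospital guideline. An efficacy analysis that drops early deaths supports neither well.

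**Working it through.** **1. The plan's own figure.** Under Determination of sample Size, 60 patients with 10% dropout "provide 80% power to detect a difference in time to recovery between arms of 3 days assuming a SD of 4 days". With 60 × 0.9 = 54 evaluable, 27 per arm, and a two-sided 0.05 test (sidedness is not stated):

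- SE = 4 × √(2/27) = 1.089; 3/1.089 = 2.756; power = Φ(2.756 − 1.96) = 0.787.

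The stated 80% reproduces to within rounding, so the sizing assumes that about 6 patients are lost.

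**2. Expected deaths.** In section 3, Preliminary Results, 23% of the sponsor's cohort had low serum zinc. Mortality was 21% in that group and 5% in the comparison group. Assuming that the other 77% die at 5%:

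- 0.23 × 0.21 + 0.77 × 0.05 = 0.0483 + 0.0385 = 0.0868.
- 0.0868 × 30 = 2.6 deaths per arm, or about 5 of 60. At 5% to 21% mortality the range is 1.5 to 6.3 per arm.

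**3. Control progression rate seen per protocol.** The plan assumes 20%. If a fraction d of patients die before Day 14 and are part of that 20%, removing them gives (0.20 − d)/(1 − d).

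| Deaths before Day 14 | Calculation | Rate seen |
|---|---|---|
| 8.7% (all) | 0.1132/0.9132 | 12.4% |
| 5% (all) | 0.150/0.950 | 15.8% |
| 4.3% (half of 8.7%) | 0.1566/0.9566 | 16.4% |
| 2.2% (a quarter of 8.7%) | 0.1783/0.9783 | 18.2% |

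The first two rows are shifts of 7.6 and 4.2 points. The plan's target is 5%, read here as percentage points.

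**4. Effect on the comparison.** The shift in step 3 is in the level of one arm. If both arms lose the same deaths, the difference changes little: 20% against 15% with 8.7% deaths in each becomes 12.4% against (0.15 − 0.0868)/0.9132 = 6.9%, a gap of 5.5 points. The damage comes when exclusions differ between arms.

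- *Hiding a benefit.* Suppose zinc halves deaths (8.7% to 4.3%) and the patients saved do not progress. The true rates are 15.7% and 20%, a 4.3-point benefit. Per protocol they appear as (0.1566 − 0.0434)/0.9566 = 11.8% and 12.4%, a gap of 0.6 points.
- *Creating a benefit.* With no effect (6/30 in each arm), suppose the 3 patients lost from zinc all progressed and the control losses are random. The result is 3/27 = 11.1% against 20%, a false benefit of 8.9 points.

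**5. Recovery time.** Normal data, SD 4, 30 per arm, t test, 100,000 simulated trials. Which patients are lost is an assumption.

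| True effect | Slowest patients dropped (zinc, control) | Mean difference favouring zinc | Proportion significant |
|---|---|---|---|
| None | 0, 0 | 0.00 days | 5.1% |
| None | 3, 0 | 0.74 days | 12.7% |
| None | 3, 3 | 0.00 days | 8.1% |
| 3 days | 0, 0 | 3.00 days | 81% |
| 3 days | 0, 3 | 2.25 days | 60% |

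Unequal loss of three slow recoverers moves the estimate by about three quarters of a day in either direction. Equal loss leaves the mean difference unbiased but still raises the type I error.

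**The case against.** Several stronger statements are tempting, and the document does not support them.

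- *Only completers are analysed.* A reader might infer this, but the and/or in the definition keeps a patient who stops zinc early and attends at Week 2, provided the primary data are present.
- *The entry rule differs by arm.* A reader might reason that only zinc can be left unfinished. Study Design lists two weeks of standard of care as the control treatment, and the Week 2 route is identical in both arms. Unequal exclusion is plausible because treatment is open-label, but it is not written into the rule.
- *The slowest recoverers are removed.* This follows only if non-recovery at Day 28 is treated as missing. A patient still ill at Week 2 who attends is in the set. Fast recoverers who go home and miss Week 2 may also be lost.
- *A drug that saves lives would look harmful.* If zinc halved deaths and every patient saved then progressed, step 3 gives 16.4% on zinc against 12.4% on control. That needs every death before Day 14 and every patient saved to progress. The less extreme case in step 4 masks a benefit but shows no harm.

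The cohort mortality may not transfer either. It has no stated time horizon, the comparison group may not be everyone outside the low-zinc group, and the trial excludes patients with a life expectancy under 72 hours. Lower or later mortality makes the shift smaller.

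Withdrawals are said to be detailed in a separate ethics submission that is not available here, so the absence of an all-randomised analysis can be asserted only for this document.

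These points limit size and direction. They do not supply a rule for deaths or non-recovery.

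**Conclusion.** The point holds as a defect in a stated rule. The only efficacy population is per protocol, missing primary data mean exclusion, deaths before Week 2 leave all three primary endpoints, and non-recovery at Day 28 has no rule. It should be corrected before analysis.

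The size is illustrative. A fall in the control progression rate from 20% to between 15.8% and 12.4% assumes 5% to 8.7% mortality, all before Day 14 and all within the 20%. Later deaths shrink it. Bias in the treatment comparison requires exclusions that differ between arms, and its direction cannot be predicted. The document does not support a claim that the analysis favours zinc, or that it disfavours zinc.

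**What to change.** - **Population.** Make all randomised patients, analysed as allocated, the primary efficacy population and the basis of the baseline table. Keep per protocol as supportive.
- **Progression.** Count death by Day 14 as progression, at the worst level of the WHO scale.
- **Recovery.** Analyse to Day 28 with deaths kept as never recovered, either as a competing event or ranked as the worst outcome. Censor unrecovered survivors at Day 28.
- **IL-6.** After a death before Week 2 the value does not exist, so state how such patients enter the analysis, for example by worst rank. Use multiple imputation with a sensitivity analysis for other missing values.

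**Cost.** A little more analysis work, outcome status from hospital records for about 6 early leavers (10% of 60), and possibly a less favourable estimate. On the stated inputs no more patients are needed: with 30 per arm, SE = 4 × √(2/30) = 1.033 and power = Φ(2.905 − 1.96) = 0.828, against 0.787 at 27. That assumes outcomes are obtained for everyone and that the 3-day difference and SD of 4 still apply. Those inputs describe a difference in means, so the sizing paragraph should say how they relate to the new recovery analysis.
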